It is hypothesized that efficacy and safety of medical expulsive therapy, containing tamsulosin and silodosin, is almost the same and silodosin can be used with the same efficacy for the treatment of lower urinary tract calculi.

Alternative Hypothesis:

Silodosin is better than Tamsulosin in efficacy and safety.

OPERATIONAL DEFINITIONS:

STONE CLEARANCE:

Stone clearance will be defined as no evidence of stone on follow up X-ray KUB imaging at 4 weeks .

ANCILLARY PROCEDURES:

Additional urological procedures needed to remove the same stone for which medical expulsive therapy was given if it fails to remove the stone completely.

SIDE EFFECTS:

Any undesirable effect noticed after prescription of the drug including but not limited to abnormal ejaculation, headache, orthostatic hypotension, backache and gastritis etc.

MATERIALS AND METHODS:

STUDY DESIGN:

Prospective randomized control trial.

STUDY SETTING:

Outpatient department of Sir Ganga Ram hospital, Lahore.

DURATION OF STUDY:

18 months.

DURATION OF TREATMENT:

Four weeks.

SAMPLE SIZE:

Using the open-epic software, the sample size was estimated. The minimum sample size that we require is 208 patients with ureteric stone who fulfil the inclusion criterion with 104 in one group receiving tamsulosin and 104 in silodosin group (1:1 ratio) with an inflation of 10 percent for estimated loss to follow up, with an anticipated expulsion rate ranging from 58-64 percent in tamsulosin group and 78-83 percent in silodosin group with a risk difference of 19 to achieve a power of 80 percent and a level of significance of 5 percent.

SAMPLING TECHNIQUE:

Patients visiting the outpatient department of Sir Ganga Ram hospital will be selected by simple random sampling, fulfilling the inclusion criteria.

SAMPLE SELECTION:

Adult male and female patients fulfilling the inclusion criteria will be assigned into two groups by random allotment, 1^{st} group will be given Tamsulosin and 2^{nd} group will be given Silodosin for four weeks.

INCLUSION CRITERIA:

Following factors make up the inclusion criteria for this study.

- Patients between ages 18 years 55 years.
- Solitary unilateral ureteral stone
- Stone sizes less than 10 mm measured on non-contrast computed tomography of kidney, ureter and bladder.
- Stones being treated primarily with medical expulsive therapy
- Radio opaque Stone

EXCLUSION CRITERIA:

The presence of following factors will exclude the patients from our study:

- Pregnancy
- Untreated UTI

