- Bleeding disorders
- Obstruction distal to stone
- Serum Creatinine > 1.3 mg/dl in males and > 1.2 mg/dl in females.
- Congenital renal anomaly/ skeletal malformation
- Previous treatment for the same stone (PCNL/ URS / push back)
- Solitary Kidney
- Prior JJ stent insertion
- Bilateral ureteral stone

DATA COLLECTION AND PROCEDURE:

The protocol will be submitted to Ethical review committee for review and only once the permission is granted, the study will be started. Patients will undergo standard procedure like detailed history taking, examination and routine investigations. Once decided that the patient will undergo MET, the patient will be explained in detail about medications, their potential side effects, follow up and the potential indications for early follow up. Our study will not change any standard process in place except the randomization between Tamsulosin and Silodosin. The data will be kept confidential as a top priority. Only principal investigator and co-principal investigator will have access to the data.

All patients as per inclusion and exclusion criteria as described above will be included in the study. The CT scan (non contrast computed tomography) will be done on (machine parameters at Ganga ram). Only patients with radioopaque stones will be included. Patients falling into the inclusion criteria will be explained about the study and once they agree to participate in study, randomization will be done. Demographic data including patients' age and comorbid, stone-related data including size, location, laterality and number of stones and duration of symptoms will be recorded. The patient will be given either Capsule Tamsulosin 0.4 mg once daily at night or Tablet Silodosin 8 mg once daily at night based on the group assigned. The patient will also be explained about the reasons for follow up earlier than four weeks including fever, persistent pain or gross hematuria. The patients will be called for follow up at 4 weeks with an X-ray KUB without bowel preparation. We will note if the stone has passed or not.

ETHICAL CONSIDERATION:

The funds for supporting this research will be provided by department of pharmacology and therapeutic FJMU, Lahore. Informed consent will be taken from patients prior to research.

DATA ANALYSIS PROCEDURE:

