Data will be entered and analyzed on SPSS version 22. Percentages and frequencies will be calculated for the demographic variables of the patients. The comparison of the two groups will be made by using T- test. P-value of less than 0.05 will be considered significant and the power used will be 0.80.

RESULTS

Frequency and percentage of demographic data

Variables		Frequency	Percentage	
Gender	Male	105	58.7	
	Female	74	41.3	
Income	Less than	108	60.3	
status	50000			
	50000 -150000	69	38.5	
	Greater than	2	1.1	
	150000			
	Normal	166	92.7	
BMI	Obese	13	7.3	
	None	136	76.0	
Comorbidity	HTN	33	18.4	
	Diabetes	10	5.6	

This information sheds light on the sample population's health and demographic distribution, showing a preponderance of people with normal BMIs and lower income levels, as well as a significant percentage of people without comorbid diseases.

In our study there are total 179 patients out of which 74 are females (41.3%) and 105 males (58.7%).

The income, 108 people, or 60.3% of the total, make less than 50,000Rs in month. Just 2 members, or 1.1 percent, make more than 150,000 monthly, while 69 participants (38.5%) have monthly salaries between 50,000 and 150,000.

13 persons (7.3%) are classed as obese, while 166 people (92.7%) have a normal BMI. These numbers represent a sizable fraction of the sample. In terms of comorbidities, 136 individuals (76.0%) state they have no comorbid conditions. Of the people with comorbidities, 10 (5.6%) had diabetes, and 33 (18.4%) had hypertension (HTN).

[figure not shown]

Figure 1: Pie chart of patients using Silodosin and Tamsulosin (Medicine Advised)

Use of medicine (Figure 1)

Tamsulosin and Silodosin, the two drugs prescribed to a group of patients, are distributed as shown in the pie chart. Of the patients, 43% were advised to take Tamsulosin, which is shown as the blue section on the chart. And (57%) of the patients were advised to take silodosin, as shown by the red segment.

Table2: Patient demographic characteristics and study variables are

Varibales	Tamsulosin	Silodosin	p-value	
Body Mass index	Normal	72(43.4%)	94(56.6%)	0.730
	obese	5 (38.5%)	08(61.5%)	
Laterality	Right	65(55.6%)	52(44.4%)	0.001
	Left	12(19.4%)	50(80.6%)	
Symp To CT	Less than 1 week	67(64.4%)	37(35.6%)	
	More than 1 week	10(15.2%)	56(84.8%)	0.001
	More than 2 week	0 (0.0%)	09(100%)	
Posl n Ureler	Proximal	28(51.9%)	26(48.1%)	

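### The clearance definition does not ask how the stone left, so a patient whose stone was taken out by a procedure before week 4 would meet the definition of success

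*Combined protocol and SAP*

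**What the plan says.** The section on operational definitions gives the efficacy rule: "Stone clearance will be defined as no evidence of stone on follow up X-ray KUB imaging at 4 weeks". Ancillary procedures are defined in the next entry as follows: "Additional urological procedures needed to remove the same stone for which medical expulsive therapy was given if it fails to remove the stone completely". That term is not used again. It is absent from the clearance rule, from the data analysis procedure and from the results.

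The section on data collection and procedure tells patients the "reasons for follow up earlier than four weeks including fever, persistent pain or gross hematuria" and says that "Our study will not change any standard process in place except the randomization between Tamsulosin and Silodosin". It then words the outcome a second way: "We will note if the stone has passed or not".

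The data analysis procedure offers only this on the comparison: "The comparison of the two groups will be made by using T- test". It has no rule for a patient who had a procedure before the film.

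The sample size section is written in terms of expulsion: "anticipated expulsion rate ranging from 58-64 percent in tamsulosin group" and "78-83 percent in silodosin group", with a difference of 19 points. The rationale likewise concerns how often stones are expelled.

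**The concern.** The trial is sized on expulsion under a drug but scored on whether a stone is visible on a film at week 4. The two agree only if every stone that is gone by week 4 left without a procedure.

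The plan leaves room for exceptions. Patients are told to come back early for certain symptoms, usual care is unchanged, and a procedure for failed expulsive therapy is a defined term. A patient who returns in week 2 and has the stone removed would have an empty film at week 4 and would satisfy the definition. That patient is a failure of the therapy under test.

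At stake are both clearance rates, the difference between them, and any time-to-expulsion analysis in which the date of a procedure might be entered as the date of expulsion.

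**Working it through.** **Inputs.** From the sample size section: expulsion 58–64% on tamsulosin and 78–83% on silodosin, a difference of 19 points, 80% power, 5% significance, 104 per arm including 10% for loss. Sidedness is not stated; I take it as two-sided. The share q of drug failures that have a procedure before week 4 is not in the documents and is an assumption throughout.

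**Step 1: the plan's own figure.** With p̄ the mean of the two rates and Δ their difference, the usual two-proportion formula is

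n = [1.96·√(2p̄(1−p̄)) + 0.84·√(p₁(1−p₁) + p₂(1−p₂))]² / Δ².

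- 59% v 78%, no continuity correction: 93 per arm; 93/0.90 = 103.3, so 104.
- 64% v 83%, with continuity correction: 94 per arm; 94 × 1.10 = 103.4, so 104.

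Both pairs lie in the stated ranges, differ by 19 points and give 104 per arm. The 208 therefore reproduces, and this point does not alter it.

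**Step 2: what the literal rule records.** If p is the true expulsion rate, recorded clearance is p + q(1−p). With the same q in both arms, the recorded difference is (p₂ − p₁)(1 − q). From 61% v 80%:

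- q = 10%: 64.9% v 82.0%, difference 17.1 points.
- q = 30%: 72.7% v 86.0%, difference 13.3 points.
- q = 50%: 80.5% v 90.0%, difference 9.5 points.

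**Step 3: power under equal q.** Power is Φ{[Δ√n − 1.96·√(2p̄(1−p̄))] / √(p₁(1−p₁) + p₂(1−p₂))}, using the recorded rates. For example, with 61% v 80%, q = 20% and n = 104, the recorded rates are 68.8% v 84.0%. Then (0.152 × 10.198 − 1.96 × 0.6005) / 0.5908 = 0.63, which gives 74%. Over the pairs from 59% v 78% to 64% v 83%:

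| q | Difference (points) | Power, 104 per arm | Power, 94 per arm (after 10% loss) |
|---|---|---|---|
| 0 | 19.0 | 84–88% | 81–85% |
| 10% | 17.1 | 79–83% | 74–79% |
| 20% | 15.2 | 72–77% | 67–73% |
| 30% | 13.3 | 64–70% | 60–65% |

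**Step 4: unequal q.** From 61% v 80%:

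- 30% on tamsulosin, 10% on silodosin: 61 + 0.30 × 39 = 72.7; 80 + 0.10 × 20 = 82.0; difference 9.3 points.
- 10% on tamsulosin, 30% on silodosin: 61 + 0.10 × 39 = 64.9; 80 + 0.30 × 20 = 86.0; difference 21.1 points.

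In general the recorded difference widens when 20·q(silodosin) exceeds 39·q(tamsulosin), that is, when the silodosin share is more than 39/20 = 1.95 times the tamsulosin share.

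**Step 5: do the results settle it?** The time-for-removal rows total 6 + 14 + 57 = 77 on tamsulosin and 52 + 37 + 13 = 102 on silodosin. All 179 analysed patients thus have a removal time within 28 days, against planned failure of 36–42% and 17–22%. For early procedures alone to produce 100% at the planned rates, p + q(1−p) = 1 requires q = 1 in both arms. Leaving failures out of the table would give the same picture. The table cannot tell the two apart.

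**The case against.** The strongest reply is that the plan's intent is clear enough. An ancillary procedure is by definition something needed when the therapy fails, so a procedure marks failure. The data collection section asks whether the stone passed, and the sample size speaks of expulsion. Treatment lasts four weeks and procedures are tied to its failure, so they may have been expected only after the week-4 film; no passage describes an earlier one. This stands as evidence of intent. It does not supply a scoring rule, and the only sentence that defines the endpoint has no such condition.

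A reader might go further and infer from the 179 removal times, or from the wording that stones were removed, that procedures were in fact counted as successes. The documents do not support that. They use removal for drug-induced passage throughout, and the text with the bar chart calls the same kind of time bands expulsion. The abstract reports 16 patients excluded for premature end of study, without reasons. Patients with early procedures could be among them, and that would be a bias from exclusion after randomisation.

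A reader might also infer that the rule must dilute the difference, because the less effective arm has more failures. That holds when q is similar in the two arms; Step 4 shows that it need not hold otherwise.

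**Conclusion.** The point holds as a defect in the written definition. A patient cleared by a procedure before week 4 would meet it, and nothing else in the plan overrides it. Because it governs the efficacy outcome and one sentence repairs it, it should be corrected.

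Its practical size is unknown. With equal q, the loss is 19q points: about 2 at q = 10%, 6 at 30% and 10 at 50%. Power at 104 per arm falls below 80% across the whole planned range by q = 20%. With unequal q, the difference can shrink or grow. All of these figures rest on assumed values of q and on expulsion rates within the plan's ranges. Whether any patient was scored this way, and how many had early procedures, cannot be determined from the documents.

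**What to change.** Define clearance as no stone on X-ray KUB at 4 weeks with no ancillary procedure performed for that stone since randomisation. Use the same wording where the data collection section records whether the stone passed. Then:

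- Score a procedure performed before week 4 as not cleared. A referral alone should not count, since a referred patient may still pass the stone unaided.
- In the time analysis, treat such a patient as not expelled by day 28, or treat the procedure as a competing event. Never enter it as an expulsion.
- Record the date and type of each ancillary procedure and report counts by arm.
- State whether any of the 16 patients excluded for premature end of study had one.
- Re-score existing patients where records allow.

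The change affects scoring only and leaves patient care, the 19-point target and the 208 patients as they are. The cost is one sentence in the definition and a check of records. Both clearance rates may fall, by an amount that the documents do not allow to be stated.

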All things considered, the thorough examination of the exclusions, withdrawals, and reported adverse effects in the pooled analysis sheds light on the difficulties and conclusions that have been found in a number of research. It emphasizes how crucial it is to closely monitor participant outcomes and unfavorable occurrences in clinical research in order to guarantee the efficacy and safety of the medicines being studied(30).

The treatment for distal ureteral stones with size less than 10 mm with tamsulosin and silodosin has resulted in a high output rates of 57-64% and 80 - 84%, respectively, according to randomized controlled studies. Nonetheless, compared to other trials, the tamsulosin success rate in those investigations is somewhat lower (31). However, tamsulosin demonstrated an 86% success rate in a randomized controlled study with almost 3000 patients(32). Tamsulosin has a 67–90.7% success rate in treating distal ureteral stones, according to Tao

et al.'s meta-analysis.20 The current study's tamsulosin success rates align with some studies (33).

Similar to the current investigation, the comparable rates in the Imperatore et al. study were 82% and 88%, and in the Arda et al. study they were 72.4% and 78.6%. These investigations also revealed no discernible difference between tamsulosin and silodosin. However, only young/middle-aged men were included in this study, whereas both of other investigations included both men and women. This sums up the main distinction between prior studies and the present investigation (34).

Tamsulosin is used commonly in our population for MET however Silodosin, a newer drug, is not used frequently for this purpose and is still under research. Also, comparison of Silodosin and Tamsulosin has not been explored in our population earlier.

Rationale

The purpose of this study is to examine and compare the effectiveness of silodosin and tamsulosin in medical expulsive therapy (MET) in terms of the rate at which stones are expelled from the body, as well as the adverse effect profiles in our patient group.

OBJECTIVES:

To evaluate and compare the efficacy and safety of medical expulsive therapy containing tamsulosin and silodosin, specifically.

To compare the side effect profile of tamsulosin and silodosin when given for medical expulsive therapy.

HYPOTHESIS:

Null Hypothesis:

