A meta-analysis was carried out on the similar comparison and it showed that mean stone ejection time was shorter in patients receiving silodosin 8 mg daily compared to those directed to drink 2 L of water daily and a greater rate of stone ejection. Meta-analyses conducted since the silodosin RCT have demonstrated that efficacy of silodosin is more than that of tamsulosin for the Medical expulsive therapy of ureteral stones. The meta analyses discovered that silodosin, as opposed to tamsulosin, dramatically raised the expulsion rate of distal ureteral stones in a meta-analysis involving five RCTs(44).

A positive but weak link was seen when the length of stone ejection was analyzed in relation to the frequency of renal colic episodes, the dosage of analgesics, and the size of the stone (Table 4; P<0.001). The number of renal colic episodes and the dose of analgesics were found to be positively and strongly correlated (P<0.001), the number of renal colic episodes and stone size was found to be positively and weakly correlated (P=0.015), and the analgesic dosage and stone size was found to be positively and to be positively and weakly correlated (P<0.05)(28).

Overall, compared to 30% of patients in the placebo group, 37.5% of patients in the tamsulosin group experienced drug-related side events (p = 0.7). The most often reported side effect was dizziness, which was more common with tamsulosin (25%) than with placebo (22.5%) (p = 0.9). Other adverse effects (sinus pressure, nosebleed, nausea, tinnitus, hands and feet swelling) that may or may not be related to the medication were recorded in isolated cases. In neither group were there any significant side effects noted. However, men in the tamsulosin group experienced ejaculatory dysfunction more frequently [5 (17.9%) vs. 1 (3.5%), (p = 0.1)].

Because both medications are safe and well tolerated, no significant side effects were seen in the trial. In groups A and C, anejaculation was experienced by 17 out of 23 patients (73.9%) and 21 out of 25 patients (84%) respectively; nevertheless, none of the patients stopped receiving treatment. After the treatment was discontinued, the situation rapidly improved. In the study patients, there was no significant change in their blood pressure or pulse rate. A study of the literature supports the findings, showing no correlation between changes in blood pressure or heart rate and a 50 mg dose of mirabegron(45).

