Our Patients on tamsulosin accounted for 40.1% of those who did not report any side effects; those on silodosin made for a larger percentage (59.9%). This implies that, in comparison to Tamsulosin, Silodosin may have a marginally higher correlation with patients reporting no adverse effects.

There was no discernible difference in the reported orthostatic hypotension values of 3.6, 5.5, and 1.8% for the silodosin, tamsulosin, and placebo groups, respectively. Other side effects were noted in the silodosin, tamsulosin, and placebo groups, respectively, and included headache (3.6, 5.5, and 1.8%), dizziness (7.1, 10.9, and 3.6%), nasal congestion (1.8, 3.6, and 0), and nausea (1.8, 3.6, and 1.8%), all without a statistically significant difference. Based on the Common Terminology Criteria for Adverse Events, version 4.0, all cases were rated as grade 1(46).

The groups who took silodosin alone and the group that took silodosin plus tadalafil experienced similar side symptoms, such as headache, dizziness, backache, orthostatic hypotension, and retrograde ejaculation (Table-III). Given that P > 0.05, that was not statistically significant(41).

Examining particular side effects reveals various themes. Nine patients on tamsulosin (60.0%) and six patients on silodosin (40.0%) developed orthostatic hypotension, a condition marked by a considerable drop in blood pressure upon standing. Despite the fact that the sample size for this particular side effect is rather modest, it suggests that Tamsulosin users are more likely to have orthostatic hypotension than Silodosin users.

According to a study, the most common adverse event associated with the silodosin group was decreased or absent ejaculation. Of the patients in groups A and B, eight patients (8 were distressed, four were not, and six were distressed but could wait for their improvement) and nineteen patients (10 were distressed, four were not, and five were distressed but could wait for their improvement) experienced this adverse event most frequently(47).

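### Side effects are a stated objective, but the plan does not say how they are elicited and gives no criterion for orthostatic hypotension

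*Combined protocol and SAP*

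**What the plan says.** The Objectives include this one: "To compare the side effect profile of tamsulosin and silodosin when given for medical expulsive therapy". The alternative hypothesis also covers safety as well as efficacy.

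Under Operational Definitions, a side effect is "Any undesirable effect noticed after prescription of the drug including but not limited to abnormal ejaculation, headache, orthostatic hypotension, backache and gastritis etc". No observer, time point, question list, threshold or grading follows.

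Data Collection and Procedure provides for history, examination and routine investigations at the start, and for explaining possible side effects to the patient. It then describes one scheduled follow-up: "The patients will be called for follow up at 4 weeks with an X-ray KUB without bowel preparation". The stated action there is "We will note if the stone has passed or not". The same section says: "Our study will not change any standard process in place except the randomization between Tamsulosin and Silodosin". One drug is a capsule and the other a tablet, and no blinding is described.

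The Results and the Discussion both report that nine tamsulosin and six silodosin patients "developed orthostatic hypotension, a condition marked by a considerable drop in blood pressure upon standing". The Conclusion says silodosin has the safer profile, with fewer ejaculatory, hypotensive and headache events.

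**The concern.** A side-effect comparison between arms is only as good as the way events are found. Two of the events that matter most for these drugs depend on the method. Orthostatic hypotension is described as a fall in pressure on standing, so it needs a postural reading and a cut-off. Ejaculatory change is easily missed unless men are asked. The plan supplies neither, and by its own account adds nothing to usual care except randomisation.

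Without a common method, two clinicians can label the same complaint differently, and an event can go unrecorded because nobody asked. With no blinding described, knowledge of the drug can influence both. The Conclusion's claim of a safer silodosin profile rests on these counts.

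**Working it through.** **1. The plan's own figure.** The table of side effects by drug has four rows (tamsulosin, silodosin): none 61, 91; orthostatic hypotension 9, 6; abnormal ejaculation 2, 1; headache 5, 4. Columns sum to 77 and 102, total 179. Pearson chi-square, the sum of (observed − expected)²/expected, with for example 15 × 77/179 = 6.45 expected hypotension cases on tamsulosin, gives 3.54 on 3 df, p = 0.315. This reproduces the figure in the Results. Several expected counts are small; a Monte Carlo exact p is 0.333.

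**2. Rates per arm.** The printed percentages (60/40, 66.7/33.3, 55.6/44.4) are each drug's share of the events, not rates. Per arm:
- Orthostatic hypotension: 9/77 = 11.7% and 6/102 = 5.9%; Fisher p = 0.18.
- Headache: 5/77 = 6.5% and 4/102 = 3.9%.
- Any listed effect: 16/77 = 20.8% and 11/102 = 10.8%; Pearson p = 0.064, Fisher p = 0.090.

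**3. Ejaculation against a cited rate.** The Results give 105 men and 3 events: 3/105 = 2.9% (95% CI 0.6 to 8.1). The Discussion cites 5 men (17.9%) on tamsulosin; 5/0.179 = 27.9, so 5/28 (95% CI 6 to 37). At 17.9%, 105 × 0.179 = 18.8 events would be expected. Fisher on 3/105 against 5/28 gives p = 0.011.

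Sex by arm is not reported. Since the arms hold 77 and 102, men on tamsulosin number between 105 − 102 = 3 and 77. Comparing tamsulosin with tamsulosin, 2/77 against 5/28 gives p = 0.014. A split in proportion to arm size (assumption: 105 × 77/179 = 45 men) gives 2/45 and p = 0.10. The evidence is suggestive, and its strength depends on a split the document does not give.

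**4. Orthostatic hypotension against cited rates.** The Discussion cites 3.6% on silodosin and 5.5% on tamsulosin in one comparative trial. I take this to be the paediatric trial described earlier in the Discussion, with 56 and 55 children, because 2/56 = 3.6% and 3/55 = 5.5% fit exactly.
- Tamsulosin, 9/77 against 3/55: Fisher p = 0.36.
- Silodosin, 6/102 against 2/56: Fisher p = 0.71.
- Silodosin against the 1.3% cited from pooled US and European studies, taken as exact: P(6 or more of 102) = 0.002.

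Only the last is clearly beyond chance.

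**5. Headache as a control.** 6.5% and 3.9% here against 5.5% and 3.6% cited: no sign of poor capture.

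**6. Fragility of the overall contrast (illustration, not an estimate).** Ten more patients with an effect on silodosin alone would give 21/102 = 20.6% and remove the difference from 20.8%. Missed events on tamsulosin would raise that number.

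**The case against.** The strongest reply is that silence about a method does not show the method was poor. The list of recorded data in Data Collection and Procedure is plainly incomplete: it omits water intake, analgesic requirement and time to removal, yet the Results tabulate all three for 179 patients. The side-effect table places every patient, including 152 with none, which fits everyone having been asked. This stands. A reader might infer that events were merely volunteered or unsolicited; the documents do not say so. The word in the definition does not identify who notices, and the patient-report wording in the Results is only suggestive.

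Other stronger readings also fail:
- **Dizziness recorded as hypotension.** Dizziness appears only in the cited studies, never in this trial's data.
- **Backache mixing stone pain with drug effect.** It is in the definition, but the table rows sum to 179 without a backache case.
- **Counts tilted towards silodosin.** Both arms have hypotension point estimates above the cited rates, and no arm-specific mechanism is shown. The literature on ejaculation is mixed: the Literature Review cites one meta-analysis with more retrograde ejaculation on silodosin and another, of five trials, with no significant difference.
- **A p-value of a few in a million for ejaculation.** That treats 17.9% as exact when it comes from about 28 men.

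It is also fair that the Results call the differences possibly random and the Discussion calls the ejaculation numbers too low for firm conclusions. That caution does not reach the Conclusion. Finally, new measurements cannot repair data already collected; only the reporting part of the fix applies to those.

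**Conclusion.** The point holds as a design gap: a stated safety objective has no defined way of detecting events, no criterion for orthostatic hypotension and no specified question on ejaculation, in a trial with no blinding described. This goes beyond missing detail, because following the text as written would give an unstandardised comparison.

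The size of any resulting error is unknown. The ejaculation shortfall (2.9% against 17.9%, p about 0.01) is consistent with under-detection. It rests on a small external study, a different population, and both arms pooled against a tamsulosin rate. The hypotension rates are not clearly above the cited comparative trial and demonstrate no bias towards silodosin.

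The Conclusion's safer-profile claim is not supported by these data: it conflicts with the document's own p = 0.315 and its statement that none of the differences is significant.

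**What to change.** **For any continuation or repeat.** At the enrolment and week-4 visits already planned:
- Ask every patient the same fixed yes/no symptom list, including ejaculatory change for men.
- Take a lying and standing blood pressure.
- Label an event orthostatic hypotension only when it meets a criterion written down in advance.

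The cost is a few minutes per visit. The downside is that solicited questions raise event counts in both arms, so rates will compare less directly with studies that did not ask.

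**For the data already collected.**
- State how side effects were elicited, by whom and when.
- Report the 15 hypotension cases as postural symptoms unless a reading exists.
- Give ejaculatory events by arm with men as the denominator, and replace the row shares with rates per arm.
- Qualify the safety statement in the Conclusion so that it agrees with p = 0.315.

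This needs only a check of existing records and changes to the text and tables.
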